#### **9.14.2 Clinical Laboratory Results**

Laboratory parameters will be summarized (e.g., total bilirubin, serum creatinine). Descriptive statistics (n, mean, standard deviation, median, minimum, and maximum) as well as changes from baseline (i.e., within 24 hours before conditioning begins for the DP arm and on the day conditioning begins for the BSC arm) will be summarized by study phase and treatment received during the Prophylaxis Phase. The number and percentage of patients with abnormal values postbaseline and other summary statistics (i.e., mean, minimum, maximum, standard deviation, and number of patients) will be presented by study phase and treatment received during the Prophylaxis Phase for each laboratory parameter as per protocol schedule.

#### **9.14.3 Vital Signs Results**

For vital signs, descriptive statistics (n, mean, standard deviation, median, minimum, and maximum) will be summarized by study phase and treatment received during the Prophylaxis Phase. Changes from baseline to maximum decrease in systolic and diastolic blood pressure will also be summarized. Abnormal vital signs (to be defined in the SAP), the number and percentage of patients with any postbaseline vital sign results above and/or below specified levels, and summary statistics (i.e., mean, median, minimum, maximum, standard deviation, and number of patients) will be presented by study phase and treatment received during the Prophylaxis Phase for each vital sign as per protocol schedule.

#### **9.14.4 Physical Examinations**

A finding identified by the investigator as abnormal on the physical examination at the screening visit will be recorded on the Medical History eCRF. A clinically significant adverse change (i.e., worsening) of a physical examination finding after screening will be recorded as an AE.

#### **9.14.5 Graft-versus-Host Disease**

##### **9.14.5.1 Incidence of Acute Graft versus Host Disease**

The proportion of patients of grade 2, 3, or 4 acute GvHD, as defined in [Section 6.8.5](#) by Day +30, Day +100 and Day +180 post-HSCT will be summarized by study phase and treatment received during the Prophylaxis Phase.

##### **9.14.5.2 Incidence of Chronic Graft-versus-Host Disease**

The proportion of patients who develop chronic GvHD, as defined in [Appendix 5](#), will be summarized by study phase and treatment received during the Prophylaxis Phase.

Defibrotide (JZP-381)  
Clinical Trial Protocol: 15-007 Version 4.0

Jazz Pharmaceuticals, Inc.  
20 August 2018

---

#### 9.14.6 **Graft Failure and Time to Neutrophil and Platelet Engraftment**

Time to neutrophil and platelet engraftment will be defined as the time from the date of HSCT to the date that the criterion for neutrophil or platelet engraftment, respectively, is met (see [Section 6.8.6](#)). Kaplan-Meier curves and summary statistics (including the percent of patients achieving engraftment up to Day +100 post-HSCT) will be presented by treatment arm.

The proportion of patients with graft failure will be summarized by study phase and treatment received during the Prophylaxis Phase.

#### 9.14.7 **Karnofsky and Lansky Performance Scores**

For Karnofsky and Lansky PS, descriptive statistics (n, mean, standard deviation, median, minimum and maximum) as well as changes from baseline (unless otherwise specified) will be summarized by study phase and treatment received during the Prophylaxis Phase.

#### 9.14.8 **Concomitant Medications**

Concomitant medications will be coded using the World Health Organization Drug Dictionary (WHODRUG) and will be summarized separately using descriptive statistics.

### 9.15 **Subgroup Analyses**

Exploratory analyses of the primary efficacy, key secondary efficacy, and safety endpoints may be conducted for the following subgroups of interest:

- Patients at very high risk of developing VOD (see [Section 4.1](#))
- Patients with prior liver disease (see [Section 4.1](#) criterion [2.a.ii.a](#))
- Pediatric population ( $\leq 16$  years)

### 9.16 **Interim Analysis and Data Monitoring**

Due to uncertainties associated with the study design assumptions, specifically the background rate of events in the BSC arm and the size of the treatment effect, an interim analysis to be overseen by the DMC is planned when 70% of patients are evaluated for the primary efficacy endpoint (i.e., VOD-free survival by Day +30 post HSCT), with specific rules for efficacy stop (i.e., 1-sided  $\alpha=0.0005$ ), futility stop (i.e., conditional power  $<10\%$ ), and possible sample size re-estimation up to a maximum of 600 patients total when the conditional power is in the promising zone. Details on the content of the interim analysis and adaptive design decision rules will be provided in an interim Statistical Analysis Plan (iSAP) and specified along with the responsibilities of the DMC as part of the DMC charter.

It is expected that the prevalence of the very high risk patients and the high risk patients will be approximately 35% and 65%, respectively, at the interim analysis. The enrollment split between high risk and very high risk patients will be monitored and managed to ensure that the minimum number of patients in the very high risk category is enrolled.

Defibrotide (JZP-381)  
Clinical Trial Protocol: 15-007 Version 4.0

Jazz Pharmaceuticals, Inc.  
20 August 2018

---

## **10 DATA QUALITY ASSURANCE**

Steps to assure the accuracy and reliability of data include the selection of qualified investigators and appropriate study sites, review of protocol procedures with the investigator and associated personnel prior to the study, and periodic monitoring visits by Jazz Pharmaceuticals or its designee. Data are reviewed throughout the study through programmed checks, reports, and manual review. Any discrepancies will be resolved with the investigator or designees as appropriate.

### **10.1 Clinical Data Management**

The standard procedures for handling and processing records will be followed in compliance with 21 CFR Part 11, Food and Drug Administration (FDA) and ICH Regulations and Guidelines, Good Clinical Practices, and the Standard Operating Procedures (SOPs) of Jazz Pharmaceuticals or the contract research organization (CRO). A comprehensive Data Management Plan (DMP) will be developed to document data sources, systems, and handling.

### **10.2 Electronic Case Report Forms**

All subject data required by the protocol to be reported to the sponsor on each trial subject will be recorded by clinical site staff in eCRFs developed by Jazz Pharmaceuticals or its designee, unless such data are transmitted to the sponsor or designee electronically (e.g., central laboratory data, data from an IWRS, electronic Clinical Outcome Assessment [eCOA] data, etc.). Electronic data sources will be identified in the DMP. The Principal Investigator must review the eCRFs and provide his/her signature certifying that he/she has reviewed the data and considers them complete and accurate to the best of his/her knowledge. Regardless of who signs or completes the forms, it is the Principal Investigator's responsibility to ensure their completeness and accuracy.

### **10.3 Retention of Data**

The investigator/institution should maintain the study documents as specified in Essential Documents for the Conduct of a Trial (ICH E6 Good Clinical Practice) and as required by the applicable regulatory requirement(s). The investigator/institution should take measures to prevent accidental or premature destruction of these documents.

Essential documents should be retained until at least 2 years after the last approval of a marketing application in an ICH region and until there are no pending or contemplated marketing applications in an ICH region or at least 2 years have elapsed since the formal discontinuation of clinical development of the investigational product. These documents should be retained for a longer period if required by the applicable regulatory requirements or by an agreement with the Sponsor. It is the responsibility of the Sponsor to inform the investigator/institution when these documents no longer need to be retained.

Defibrotide (JZP-381)  
Clinical Trial Protocol: 15-007 Version 4.0

Jazz Pharmaceuticals, Inc.  
20 August 2018

---

## **11 ADMINISTRATIVE CONSIDERATIONS**

### **11.1 Investigators and Study Administrative Structure**

Parties (e.g., Sponsor, CROs, and vendors) responsible for the various functions in this study will be listed in a separate document and filed in the Trial Master File.

### **11.2 Institutional Review Board (IRB) or Independent Ethics Committee (IEC) Approval**

The final approved protocol and the informed consent form will be reviewed by the IRB/IEC. In addition, the IRB/IEC will review any other written information to be provided to the patient, advertisements for patient recruitment (if used), and patient compensation (if any). The committee's decision concerning conduct of the study will be sent in writing to the investigator and a copy will be forwarded to the Sponsor. The investigator agrees to make any required progress reports, as well as reports of SAEs, life-threatening problems, death, or any significant protocol deviations, as required by the IRB/IEC.

A list of the IRB/IEC members who actually participated in the review, their respective titles (occupational identification), and institutional affiliations or an IRB/IEC assurance number must be provided to the Sponsor. The approval letter or notice must be provided on IRB/IEC letterhead and contain the date of the meeting and sufficient information to identify the version of the protocol unambiguously (by name and number) and state that the informed consent form was also reviewed.

A clinical study may not be initiated before the proposed protocol and informed consent form have been reviewed and unconditionally approved by an IRB meeting federal regulations. The clinical study remains subject to continuing review by the IRB. The Sponsor or its designee will supply all necessary data for the investigator to submit to the IRB/IEC. The Sponsor will not ship clinical supplies to an investigational site until written signed approval from the site's IRB/IEC has been received by the Sponsor.

The investigator is responsible for ensuring initial and continued review and approval of the clinical study by the IRB/IEC at his/her site. The investigator must also ensure that he/she will promptly report to the IRB/IEC and the Sponsor all changes in the research activity and all unanticipated problems involving risk to human patients or others, and that he/she will not make any changes in the research without IRB/IEC approval, except where necessary to eliminate apparent hazards to human patients. If the study remains in progress for more than 1 year, documentation of annual renewal must be submitted to the Sponsor or its designee. Within 3 months of study completion or termination, a final report must be provided to the IRB/IEC by the clinical site.

### **11.3 Ethical Conduct of the Study**

The study will be conducted in accordance with applicable local regulations relating GCP and with the SOPs of the CRO or the Sponsor, as applicable. These standards respect the following guidelines or laws:

Defibrotide (JZP-381)  
Clinical Trial Protocol: 15-007 Version 4.0

Jazz Pharmaceuticals, Inc.  
20 August 2018

- 
- Guideline for Good Clinical Practice E6 (R1): ICH, May 1996).
  - US Code of Federal Regulations (CFR) pertaining to conduct and reporting of clinical studies (Title 21 CFR Parts 11, 50, 54, 56, 312, and 314).
  - Clinical Trials Directive (European Medicines Agency [EMA]) Directive 2001/20/EC

Endorsement of the ethical principles embedded in the above guidances and regulations ensures that the rights, safety, and well-being of study patients are protected and are consistent with the principles that have their origin in the Declaration of Helsinki, World Medical Association –“Ethical Principles for Medical Research Involving Human Subjects.”

#### **11.4 Patient Information and Consent**

All patients or their parents/legal guardians or representatives will provide their written informed consent before the performance of any study-related procedures. Study sites will follow local guidelines regarding assent of minor children.

Each patient's chart will have his/her signed ICF for study participation attached to it. When the study treatment is completed and the eCRF has been monitored, the ICF will be kept in the investigator's central study file. Regulatory authorities may check the existence of the signed ICF in this central study folder if not having done so during the performance of the trial.

#### **11.5 Patient Confidentiality**

All reports and communications relating to the patients in the study will identify each patient only by the patient's study number. These documents will be treated with strict adherence to professional standards of confidentiality and will be filed at the study site under adequate security and restricted access.

Portions of the patient's medical records pertinent to the study will be reviewed by Sponsor personnel or its designee and possibly by governmental agency personnel to ensure adequate source documentation, accuracy, and completeness of the eCRFs. The IRB has the authority to review patient records.

#### **11.6 Protocol Adherence – Amendments**

The protocol must be read thoroughly and the instructions must be followed exactly.

Any changes in the protocol will require a formal amendment. Such amendments will be agreed upon and approved in writing by the investigator and the Sponsor designees. The IRB/IEC will be notified of all amendments to the protocol. Amendments to the protocol will not be implemented until written IRB/IEC approval has been received.

#### **11.7 Required Documents**

The investigator must provide the Sponsor or its designee with the applicable regulatory documents before the enrollment of any patient (copies should be kept by the investigator in the investigator's regulatory document binder).

Defibrotide (JZP-381)  
Clinical Trial Protocol: 15-007 Version 4.0

Jazz Pharmaceuticals, Inc.  
20 August 2018

---

## 11.8 Study Monitoring

Throughout the course of the study, the study monitor will make frequent contacts with the investigator. This will include telephone calls and onsite visits. During the onsite visits, the eCRFs will be reviewed for completeness and adherence to the protocol. As part of the data verification, source documents will be made available for review by the site. The study monitor will also perform drug accountability checks and will periodically request review of the investigator study file to assure completeness of documentation in all respects of clinical study conduct.

Upon completion of the study, the study monitor will arrange for a final review of the study files after which the files should be secured for the appropriate time period. The investigator or appointed delegate will receive the study monitor during these onsite visits and will cooperate in providing the documents for review and respond to inquiries. In addition, the investigator will permit inspection of the study files by authorized representatives of the regulatory agencies.

To minimize introduction of bias into the trial we are proposing to capture via IWRS the objective measures for VOD diagnosis, which will be verified during on-site monitoring of the study. Of the 4 parameters for VOD diagnosis 2 are clinically objective (weight gain and bilirubin). For hepatomegaly and ascites, we will attempt to provide within the protocol a numerical method to quantify a diagnosis and provide guidance and education for assessment of these parameters. We will monitor the rescue treatment throughout the trial as well as investigator adherence to the pre-defined schedule of assessments. VOD cases in the BSC arm which are not confirmed by the blinded endpoint committee will be specifically reviewed for consideration of any critical protocol violations. The specific concern of patients in the BSC arm receiving defibrotide prior to a diagnosis of VOD will be addressed through training at the investigator meetings, site initiation visits and periodically reemphasized through site communication (e.g., newsletters).

## 11.9 Oversight Committees

### 11.9.1 Data Monitoring Committee

An independent DMC will oversee periodic safety analyses and one interim analysis that is part of the adaptive design of this study. Periodic safety analyses will begin after 50 patients have been randomly assigned to study treatment and monitored for a minimum of 100 days after HSCT, and will occur approximately every 6 months thereafter. The interim analysis is planned when 70% of patients are evaluable for the primary efficacy endpoint (i.e., VOD-free survival by Day +30 post-HSCT). Specific rules for efficacy stop, futility stop, and possible sample size re-estimation are outlined in the iSAP and DMC charter.

Sponsor personnel will attend and prepare presentations for the Open Sessions of the DMC. Sponsor personnel will not be involved in the statistical function for DMC assessments in this study, and data will be delivered to the DMC in a restricted manner.

The members and functions of the DMC will be detailed in the DMC Charter.

Defibrotide (JZP-381)  
Clinical Trial Protocol: 15-007 Version 4.0

Jazz Pharmaceuticals, Inc.  
20 August 2018

---

### 11.9.2 Endpoint Adjudication Committee

An independent EPAC that is blinded to study treatment assignment will be established to determine whether a patient meets the criteria for the primary efficacy endpoint (i.e., VOD-free survival by Day +30 post HSCT), the key secondary efficacy endpoint (i.e., VOD-free survival at Day +100 post-HSCT), using the modified Seattle criteria for diagnosis of VOD. The EPAC will review all available data, including relevant eCRFs, results of diagnostic procedures, and ultrasound results; alternate etiology (see [Section 6.3.1.3](#)) will also be considered during review of patient data.

The members and functions of the EPAC will be detailed in the EPAC Charter.

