### 5.6 Blinding

This is an open-label study. To minimize potential for bias, the following blinding measures will be employed:

- The central reviewer of imaging studies will be blinded to study treatment assignment and all non-radiologic patient data (see [Section 6.3.1.2](#)).
- Members of the EPAC will be blinded to study treatment assignment, will not be employees of the Sponsor, and will not be otherwise involved in the study ([Section 6.3.1.3](#) and [Section 11.9.2](#)).

Defibrotide (JZP-381)  
Clinical Trial Protocol: 15-007 Version 4.0

Jazz Pharmaceuticals, Inc.  
20 August 2018

---

Details of Sponsor blinding will be provided in a separate document.

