## **5.8 Treatment Compliance**

Defibrotide will be administered by study site personnel, and all administrations will be recorded in the eCRF. Treatment compliance will be monitored throughout the study.

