### 6.3.1.2 Central Review of Imaging Studies

All imaging studies will be reviewed at a central imaging facility by personnel who will be blinded to study treatment and all non-radiologic data.

The central imaging facility will address the following:

- Liver size (change from baseline, hepatic length in the mid-clavicular line, associated date)
- Ascites (“absent/present/not evaluable”, description, associated date);  
“Ascites present” at baseline or any post-baseline ultrasound examination is defined as the presence of any amount of free fluid greater than trace as determined by ultrasonography on the specified examination. If there is trace ascites or no ascites on a specific ultrasound examination, this is considered “ascites absent.” If the presence of ascites is not obtainable for any reason during an ultrasound examination, then the ultrasound finding for ascites will be considered “not evaluable” (see [Table 4](#) for details).

Defibrotide (JZP-381)  
Clinical Trial Protocol: 15-007 Version 4.0

Jazz Pharmaceuticals, Inc.  
20 August 2018

---

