### 6.3.1.3 Endpoint Adjudication Committee

Development of VOD for individual patients will be adjudicated by members of the EPAC, who will be blinded to study treatment. The EPAC will receive weight data, clinical laboratory test results, imaging reports from the central imaging facility, biopsy data (any organ, when available), and additional data as clinically indicated. The EPAC will base its adjudication decision on review of the following as outlined in the central imaging charter:

- Weight gain  $\geq 5\%$  from baseline (yes/no, date of assessment)
- Total bilirubin  $> 2$  mg/dL (yes/no, date of assessment)
- Imaging reports from the central imaging facility providing data regarding liver size and/or ascites
- Physical exam data (assessment of right upper quadrant pain)
- Additional data as clinically indicated
- Biopsy data (any organ)
- For hyperbilirubinemia/liver dysfunction (such as GvHD, intravascular hemolysis, viral infection(s), prior liver disease)
- For ascites and/or weight gain (fluid overload, cardiac failure, capillary leak syndrome)

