## Appendix 3 Diagnosis of Veno-Occlusive Disease by Liver Biopsy

### Introduction

Confirmation of the clinical diagnosis of veno-occlusive disease (VOD) relies on histological findings including occlusion of terminal hepatic venules and sublobular veins (Shulman et al. 1980), sinusoidal fibrosis (Jones et al. 1987), and hepatic necrosis (Shulman et al. 1980). Using necropsy data in a prospective study of 255 bone marrow transplant (BMT) recipients between 1978 and 1980, McDonald et al. found the positive predictive value of a “certain” clinical diagnosis of VOD to be 88% compared with histological confirmation of venular occlusion in the cohort of 64 patients upon autopsy (1984). Similar results were obtained from an analysis of 235 BMT recipients at Johns Hopkins in whom a cohort of 48 autopsies was evaluable for VOD (Jones et al. 1987). The positive predictive value for a certain clinical diagnosis of VOD was 95%. Of note, the negative predictive value for a certain clinical diagnosis of “no VOD” was 96% and 93% in these 2 series, respectively.

Although the expectation is that the clinical diagnosis of VOD will be the primary information provided to the Endpoint Adjudication Committee (EPAC), it is possible that liver biopsy data will be presented in a subset of patients. This appendix provides a standardized protocol for tissue preparation and analysis of key histopathological VOD features.

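### The protocol describes the adjudication committee's data package inconsistently and masks only treatment assignment, so the open-label investigator's VOD diagnosis and the start of rescue may reach the committee

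*Protocol*

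**What the plan says.** The committee's input is described in several places, and the descriptions differ.

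- Protocol 11.9.2: "The EPAC will review all available data, including relevant eCRFs, results of diagnostic procedures, and ultrasound results". Alternate etiology is also to be considered.
- Protocol 3.1 and SAP 4.1: relevant eCRFs, diagnostic procedures and ultrasound results. Protocol 3.1 adds that the committee confirms retrospectively whether the criteria were met.
- Protocol 6.3.1.3: "The EPAC will receive weight data, clinical laboratory test results, imaging reports from the central imaging facility, biopsy data". The section adds physical-examination data and possible other causes, and it leaves room for further data where clinically called for.
- Protocol Appendix 3, on liver biopsy, expects that "the clinical diagnosis of VOD will be the primary information provided to the Endpoint Adjudication Committee", with biopsy data in some patients.

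On masking, Protocol 5.6 says: "Members of the EPAC will be blinded to study treatment assignment". Protocol 11.9.2 and SAP 4.5 say the same and go no further. The central imaging reader has a stricter rule in Protocol 6.3.1.2, where studies are read "by personnel who will be blinded to study treatment and all non-radiologic data".

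Protocol 11.9.2 leaves the committee's functions to an EPAC Charter, and Protocol 6.3.1.3 refers to the central imaging charter. Neither is among the documents.

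**The concern.** The trial is open-label, and the blinded committee is its main protection against diagnostic bias. The investigator's VOD diagnosis, the date of that diagnosis and the start of rescue are not the treatment assignment. A committee that is blinded exactly as stated could still see them.

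Those items come from an investigator who knows the arm. In the BSC arm, defibrotide is meant to be given only after VOD is diagnosed (Protocol 3.1 and 5.7.6). A committee that knows VOD was called and rescue begun may lean towards confirming it. If that happened more often in the BSC arm, it would add BSC events and favour defibrotide. No planned analysis would show it clearly:

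- Sensitivity analysis V relies on the committee's assessment alone.
- The investigator-assessed analysis uses the unblinded source.
- The concordance table is not an independent check if the second assessor has seen the first one's answer.

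**Working it through.** **Step 1: what the stated masking covers.**

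| Item | Withheld from the committee as written? |
|---|---|
| Randomized arm | Yes (Protocol 5.6, 11.9.2; SAP 4.5) |
| Prophylaxis dosing records | By implication, because they reveal the arm |
| Investigator's VOD diagnosis and its date | Not stated |
| IWRS rescue registration and start of rescue defibrotide | Not stated; rescue is open to both arms, so it does not by itself reveal the arm |

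The eCRF holds treatment information: Protocol 5.8 says that "all administrations will be recorded in the eCRF". Some filter is therefore needed before eCRFs go to a blinded committee, and neither document describes one.

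**Step 2: where judgement enters.** Several components have numeric thresholds. The committee must still judge whether weight gain is unexplained (Protocol 6.3.1.1), whether another cause accounts for the findings (6.3.1.3, 11.9.2), the onset date, and whether the case is evaluable (SAP 10.1).

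**Step 3: how those judgements reach the endpoint.** Under SAP 10.1, a rescued BSC patient is censored at rescue if the committee finds no VOD, finds the case not evaluable, or dates VOD more than 3 days after rescue began. If the committee confirms VOD by Day +30 with a date no later than that limit, the patient has an event. The yes/no answer and the date both matter, and the date is compared with the start of rescue.

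**Step 4: the design figures, for scale.** These are not in dispute.

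- HR = ln(0.86)/ln(0.72) = 0.459, against 0.46 stated.
- Power at 68 events = Φ(√(68/4) × |ln 0.46| − 1.960) = Φ(3.202 − 1.960) = 89.3%, against 90% stated.

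**Step 5: an assumed illustration.** Take no true effect, 180 evaluable per arm (200 less 10% dropout), and a common event rate of 21%, the midpoint of 14% and 28%. Let adjudication add b to the BSC rate only. With p̄ the mean of the two rates,

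false-positive rate = Φ[(b − 1.960 × SE₀)/SE₁], SE₀ = √(2p̄(1 − p̄)/180), SE₁ = √((p₁(1 − p₁) + p₀(1 − p₀))/180).

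For b = 0.02 (0.23 v 0.21), SE₀ and SE₁ are both 0.0437. The argument is −1.502 and the result is 6.65%.

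| b (points) | Extra BSC events (180 × b) | False-positive rate, base 21% | Range, base 28% to 14% |
|---|---|---|---|
| 0 | 0 | 2.5% | 2.5% |
| 1 | 1.8 | 4.2% | 4.0–4.5% |
| 2 | 3.6 | 6.65% | 6.15–7.65% |
| 3 | 5.4 | 10.0% | 9.1–12.0% |
| 5 | 9.0 | 20.0% | 17.6–24.7% |

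A log-rank approximation agrees for b = 0.02. HR = ln(0.79)/ln(0.77) = 0.902, and events = 360 × 0.21 + 3.6 = 79.2. Then |ln 0.902| × √(79.2/4) = 0.459, and Φ(0.459 − 1.960) = 6.7%.

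**The case against.** The case on the other side is substantial.

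- **The committee decides for itself.** Weight gain, bilirubin and liver enlargement have numeric thresholds. Liver size and ascites must be shown by ultrasound and are read centrally under the stricter blinding. The SAP expects the committee to overrule investigators. This stands: a reader might infer that the investigator's diagnosis passes straight into the primary endpoint, and the documents do not support that. Influence on the judgement items is as far as the text goes.
- **Appendix 3 does not name the investigator.** A reader might infer that the investigator's diagnosis is the committee's main evidence. The sentence contrasts clinical with biopsy evidence and states an expectation. It does not say whose diagnosis is meant.
- **Prophylaxis dosing records.** A reader might infer that these are open to the committee. Blinding to assignment already implies that they are not, and Protocol 5.8 concerns compliance, not the adjudication packet.
- **Protocol 11.8.** It addresses BSC patients receiving defibrotide before a VOD diagnosis. That is a matter of site conduct, not of what the committee sees.
- **The charters may settle it.** This stands as a limit: silence in the protocol does not show that masking is absent. A restricted packet in the Charter would, however, conflict with the open wording of 11.9.2.
- **The size is assumed.** This stands. Rescue is open to both arms, so any influence need not fall on the BSC arm alone. The calculation is also not the planned stratified two-stage log-rank test, in which unconfirmed rescued BSC patients are censored.

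**Conclusion.** The point holds as an inconsistency with an open route for influence. The descriptions of the packet do not agree, the broadest has no stated limit, and nothing says that the investigator's VOD diagnosis, its date or the start of rescue is withheld. They could bear on etiology, onset date and evaluability, and so on the event-or-censor decision. They would also make the concordance table non-independent.

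The documents do not show that such influence occurs, in which arm, or how large it would be. The move from 2.5% to about 7% rests wholly on the assumption of 2 extra points (about 4 patients of 180) confirmed in the BSC arm only, with no true effect. If both arms were affected equally, this inflation would not arise. The Charter could already close the gap. The change is worth making because it is cheap and the committee's independence carries the primary analysis.

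**What to change.** In Protocol 11.9.2, 3.1 and 6.3.1.3 and in SAP 4.1, give one definition of the packet:

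- **Included:** weight, laboratory, central imaging, biopsy and physical-examination data, plus the eCRF data needed to assess alternate etiology.
- **Bounded:** the open-ended item for further data in 6.3.1.3, which as written means that list is not closed and cannot simply be substituted.
- **Withheld:** the investigator's VOD diagnosis and its date, the IWRS rescue registration, and all defibrotide administration, PK and immunogenicity records.

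In Appendix 3, refer to clinical findings in place of the clinical diagnosis. Align the EPAC Charter with this text.

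The cost is wording and a filter on the adjudication packet. Visits, sample size and patient care do not change. The committee loses rescue timing as context. The comparison of its VOD date with the start of rescue in SAP 10.1 can still be programmed from the database after adjudication. The filter will not remove every cue: extra ultrasounds done because VOD was suspected remain in the imaging record.
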